### **8.3.2      Method of Detecting Adverse Events and Serious Adverse Events**

Care will be taken not to introduce bias when detecting AEs and/or SAEs. Open-ended and non-leading verbal questioning of the participant is the preferred method to inquire about AE occurrence.

A consistent methodology of non-directive questioning should be adopted for eliciting AE information at all participant evaluation time-points.

### **8.3.3      Follow-Up of Adverse Events and Serious Adverse Events**

#### **8.3.3.1      Investigator Follow-Up**

The Investigator should follow each adverse event until the event has resolved to baseline grade or better, the event is assessed as stable by the Investigator, the event is otherwise explained, the participant is lost to follow-up (Section [7.3](#)), or the participant withdraws consent. Every effort should be made to follow all SAEs considered to be related to study treatment or trial-related procedures until a final outcome can be reported.

During the study period, resolution of AEs (with dates) should be documented on the Adverse Event eCRF and in the participant's medical record to facilitate source data

verification. If, after follow-up, return to baseline status or stabilization cannot be established, an explanation should be recorded on the Adverse Event eCRF.

All pregnancies reported during the study should be followed until pregnancy outcome and reported according to the instructions provided in Section [8.3.5](#).

### **8.3.3.2      Sponsor Follow-Up**

For SAEs, non-serious AEs of special interest, and pregnancies, the Sponsor or a designee may follow up by telephone, fax, electronic mail, and/or a monitoring visit to obtain additional case details and outcome information (e.g., from hospital discharge summaries, consultant reports, autopsy reports) in order to perform an independent medical assessment of the reported case.

### **8.3.4      Regulatory Reporting Requirements for Serious Adverse Events**

Prompt notification by the Investigator to the Sponsor of a SAE is essential so that legal obligations and ethical responsibilities towards the safety of participants and the safety of a study treatment under clinical investigation are met.

The Sponsor has a legal responsibility to notify both the local regulatory authority and other regulatory agencies about the safety of a study treatment under clinical investigation. The Sponsor will comply with country-specific regulatory requirements relating to safety reporting to the regulatory authority, IRB/ IEC, and investigators.

Investigator safety reports must be prepared for suspected unexpected serious adverse reactions (SUSAR) according to local regulatory requirements and Sponsor policy and forwarded to investigators as necessary.

An investigator who receives an investigator safety report describing a SAE or other specific safety information (e.g., summary or listing of SAEs) from the Sponsor will review and then, file it along with the Investigator's Brochure and will notify the IRB/IEC, if appropriate according to local requirements.

For immediate and expedited reporting requirements from Investigator to Sponsor and from Sponsor to Health Authority, investigators, IRB and EC, see [Appendix 2](#).

### **8.3.4.1      Emergency Medical Contacts**

To ensure the safety of study participants, access to the Medical monitors is available 24 hours a day 7 days a week. Details will be available on a separately.

### **8.3.5      Pregnancy**

Female participants of childbearing potential will be instructed to immediately inform the Investigator if they become pregnant during the study or within 56 days after the last dose of study treatment.

Male participants will be instructed through the ICF to immediately inform the Investigator if their partner becomes pregnant during the study or within 56 days after the last dose of study drug.

If a pregnancy is reported, the Investigator should inform the Sponsor within 24 hours of learning of the pregnancy and should follow the pregnancy reporting process as detailed in [Appendix 5](#).

Abnormal pregnancy outcomes (e.g., spontaneous abortion, fetal death, stillbirth, congenital anomalies, ectopic pregnancy) are considered SAEs ([Appendix 5](#)).

### **8.3.6 Non-Serious Adverse Events of Special Interest**

Non-serious adverse events of special interest are required to be reported by the Investigator to the Sponsor immediately (i.e., no more than 24 hours after learning of the event; see [Appendix 2](#) for reporting instructions).

Non-serious adverse events of special interest for this study include the following:

- NCI CTCAE (v5.0)  $\geq$  G2 hypersensitivity reaction/ *IRR*.
- Cases of an elevated alanine aminotransferase (ALT) or aspartate aminotransferase (AST) in combination with either an elevated bilirubin or clinical jaundice, as defined in [Appendix 3](#).
- Suspected transmission of an infectious agent by the study treatment, as defined below:

Any organism, virus, or infectious particle (e.g., prion protein transmitting transmissible spongiform encephalopathy), pathogenic or non-pathogenic, is considered an infectious agent. A transmission of an infectious agent may be suspected from clinical symptoms or laboratory findings that indicate an infection in a patient exposed to a medicinal product. This term applies only when a contamination of the study treatment is suspected.

### **8.3.7 Disease-Related Events and/or Disease-Related Outcomes Not Qualifying as AEs or SAEs**

Not applicable for the participants in this study.

### **8.3.8 Management of Specific Adverse Events**

Treatment of AEs will be considered on a case-by-case basis according to local standard of care.

*For participants who report AEs of systemic IRRs or systemic hypersensitivities, following the first occurrence of an event, pre-medicate with paracetamol and antihistamine (as per local guidelines) prior to next administration of study treatment. At the reporting of an AE of systemic IRR or hypersensitivity, the Sponsor must be contacted.*

*If a subsequent systemic IRR or hypersensitivity AE occurs, stop dosing in this participant (see Section 4.1.4).*

## **8.4 TREATMENT OF OVERDOSE**

Study treatment overdose is the accidental administration of a drug in a quantity that is higher than the assigned dose. An overdose or incorrect administration of study treatment is not an AE unless it results in untoward medical effects (see Sections 5 and 5.2 of [Appendix 2](#) for further details).

Any study drug overdose or incorrect administration of study drug should be noted on the Study Drug Administration eCRF.

All AEs associated with an overdose or incorrect administration of study drug should be recorded on the Adverse Event eCRF.

In the event of a dose administration error, the Investigator should:

1. Contact the Sponsor's Medical Monitor immediately.
2. Closely monitor the participant for AE/SAE and laboratory abnormalities until resolved.
3. Obtain a blood sample for PK analysis as soon as possible from the time of the last dose of study treatment, if requested by the Medical Monitor (determined on a case-by-case basis).
4. If known, document the variance from planned dose administration, in the CRF.

## **8.5 PHARMACOKINETICS**

Blood samples will be collected to determine serum concentration of RO7049665. Samples will be collected at the timepoints specified in the Schedules of Activities (Section 1.3) and at any time point when an ADA sample is taken (Section 8.2.6).

The date and time of each sample collection will be recorded in the eCRF. Serum RO7049665 concentrations will be measured using validated specific enzyme-linked immunosorbent assay (ELISA). If deemed appropriate, samples may also be assayed with non-validated exploratory methods.

During the course of the study, PK sampling time-points may be modified and/or up to 3 additional PK samples may be collected per participant on the basis of emerging data in order to allow for optimal characterization of the PK profile of RO7049665, after agreement with the Sponsor's clinical pharmacologist and the investigator.

Additional PK samples will be taken at the time of treatment discontinuation, at time of ADA sample collection if additional ADA samples are collected, and if the participant experiences an infusion-related AE (such as an injection-related reaction [IRR]).

Samples collected from placebo-treated participants will not be analyzed in the first instance, but retained for subsequent analysis if appropriate.

Any volume of blood samples remaining after the specified analyses may also be used for additional assay development or study or compound-specific validation experiments (e.g., for PK Parallelism Assessment and ADAs).

Samples will be destroyed within 2 years after the date of final clinical study report (CSR).

Details on sampling procedures, sample storage and shipment are given in the Sample Handling Manual.

## **8.6 PHARMACODYNAMICS**

Samples will be collected for PD assessments at the time points specified in the SOA (Section 1.3). The date and time of each sample will be recorded in the eCRF.

### **Blood samples**

Blood samples will be collected for the following assessments:

- To quantify relative and absolute WBC counts (T cells, B cells, NK cells, and eosinophils) by flow cytometry as well as complete white blood count differential. Tests include (but are not limited to) markers for quantification and characterization of  $T_{reg}$ s and  $T_{eff}$  cell subsets CD3, CD4, CD8, CD25, CD127 and FoxP3.
- Additional blood samples will be collected for potential evaluation of T cell subset specific methylation signature changes induced by drug. Decision to perform this exploratory assessment involving deoxyribonucleic acid (DNA) extraction will be made based on emerging PD data.

### **Tissue samples**

Tissue colon biopsy samples will be collected for the following assessments:

- To characterize infiltrating WBCs by histology (hematoxylin and eosin staining) and immunohistochemistry (IHC). IHC markers tested may include but are not limited to CD3, CD4 and FoxP3.
- RNA extraction on tissue colon biopsy samples may be performed in order to undertake optional whole or targeted transcriptome gene expression analysis.
- Bacterial DNA or RNA may be extracted for subsequent mucosa-associated metagenomic analysis.
- Methylation signature changes induced by drug indicative of quantitative and specific changes of T cell subsets may be assessed. The decision to perform this exploratory assessment involving DNA extraction will be made based on emerging PD data.

## **Serum and plasma samples**

Serum and plasma samples will be collected for the following assessments:

- To measure cytokines or cytokine receptors mechanistically linked with the drug's mode of action. Soluble biomarkers considered for testing include, but are not limited to, IL-5, IL-6, IL-8, IL-10 and sCD25. The final panel of soluble biomarkers will be informed by the outcome of the EIH study (WP39826) and the analysis of the resulting biomarker data, as well as by emerging data obtained in study WP40161.
- Cytokines IL-6, IL-8, TNF- $\alpha$  or IL-1b may in addition be measured as exploratory safety biomarkers ad hoc in participants experiencing symptoms associated with injection-related reactions.
- Exploratory disease biomarkers with potential for patient stratification or non-invasive response to treatment may be tested including, but not limited to perinuclear anti-neutrophil cytoplasmic antibody (pANCA) and Leucine-rich Alpha-2 Glycoprotein (LRG)
- Additional soluble biomarkers to obtain further confidence on mechanism of action of RO7049665 in humans, PD or disease markers may be tested.

## **Stool samples**

Stool samples will be collected to evaluate exploratory disease biomarkers with potential for patient stratification or non-invasive response to treatment monitoring including but not limited to faecal Calprotectin.

## **Leftover biological samples**

Any remaining stool, serum, plasma, blood or colon biopsy sample after the specified analyses may also be used for additional method, study or compound specific (assay) validation experiments or biomarker measurements. The stool, serum, plasma samples, and tissue colon biopsy samples will be destroyed within 5 years after the date of final CSR. For participants who consent to RBR, leftover samples will be transferred to RBR (see Section 8.8.2.1).

## **8.7 GENETICS**

### **8.7.1 Clinical Genotyping**

A mandatory whole blood sample will be taken for DNA extraction from every participant in all countries where this assessment is permitted (See SoA Section 1.3). The DNA may be used for, but analysis is not limited to:

- Genotyping of alleles in genes encoding proteins involved in IL 2-mediated signal transduction
- Genotyping of alleles in genes, for which genetic polymorphisms have been previously associated with autoimmune diseases.

Data arising from all biosamples including samples for analyses of inherited DNA will be subject to the confidentiality standards described in Section 1.4 of [Appendix 1](#).

Any remaining blood sample after the specified analyses may also be used for additional method, study or compound (assay) validation experiments.

The DNA or blood samples will be destroyed within 5 years after the date of final CSR. For participants who consent to RBR, leftover blood and DNA samples will be transferred to RBR (see Section [8.8.2.1](#)).

Details on processes for collection and shipment of these samples can be found in Sample Handling Manual.

## **8.8 BIOMARKERS**

Samples will be collected for biomarker assessments at the time points specified in the Schedules of Activities (Section [1.3](#)). Biomarkers will be evaluated as described in Sections [8.6](#), and [8.7](#).

### **8.8.1 Exploratory Disease Biomarkers**

Exploratory disease biomarkers will be tested for their ability to stratify participants or to evaluate their potential for non-invasive response to treatment monitoring. Markers to be tested may include, but are not limited to perinuclear anti-neutrophil cytoplasmic antibody (pANCA), LRG, and faecal Calprotectin.

### **8.8.2 Samples for Research Biosample Repository**

#### **8.8.2.1 Overview of the Research Biosample Repository**

The Roche Research Biosample Repository (RBR) is a centrally administered group of facilities for the long-term storage of human biologic specimens, including body fluids, solid tissues, and derivatives thereof (e.g., DNA, RNA, proteins, peptides). The collection, storage and analysis of these specimens will facilitate the rational design of new pharmaceutical agents and the development of diagnostic tests, which may allow for individualized drug therapy for participants in the future.

For participants who consent to RBR, leftover samples will be transferred to RBR.

Leftover specimens will be used to achieve the following objectives:

- To study the association of biomarkers with efficacy, AEs, or progressive disease.
- To increase knowledge and understanding of disease biology.
- To study treatment response, including drug effects and the processes of drug absorption and disposition.
- To develop biomarker or diagnostic assays and establish the performance characteristics of these assays.

- To enable further exploratory biomarker research.

### **8.8.2.2      Sample Collection**

The following samples will be stored in the RBR and used for research purposes, including, but not limited to, research on biomarkers related to study treatment, target and/or disease:

- Leftover plasma samples
- Leftover serum samples
- Leftover colon biopsy (and any derivatives) samples
- Leftover blood samples for DNA extraction
- Leftover extracted RNA and DNA samples
- Leftover stool samples

The samples collected for DNA extraction include, but are not limited to, genomic analysis and may be sent to one or more laboratories for analysis of germline or somatic mutations via whole genome sequencing (WGS), whole exome sequencing (WES), next-generation sequencing (NGS), or other genomic analysis methods.

Genomics is increasingly informing researcher's understanding of disease pathobiology. WGS provides a comprehensive characterization of the genome and, along with clinical data collected in this study, may increase the opportunity for developing new therapeutic approaches. Data will be analyzed in the context of this study but will also be explored in aggregate with data from other studies. The availability of a larger dataset will assist in identification of important pathways, guiding the development of new targeted agents.

Samples may be sent to one or more laboratories for analysis for WGS and other genomic analyses and associated clinical data may be shared with researchers who are not participating in the study or submitted to government or other health research databases for broad sharing with other researchers. Participant will not be identified by name or any other personally identifying information. WGS data will be analyzed in the context of this study but will also be explored in aggregate with data from other studies to increase researcher's understanding of disease pathobiology and guide the development of new therapeutic approaches. Given the complexity and exploratory nature of these analyses, WGS data and analyses will not be shared with investigators or study participants unless required by law.

For all samples, dates of consent and specimen collection should be recorded on the associated RBR page of the eCRF. For sampling procedures, storage conditions, and shipment instructions, see the separate Laboratory Manual.

RBR specimens will be stored and used until no longer needed or until they are exhausted. The Research Biosample Repository storage period will be in accordance

with the IRB/EC-approved Informed Consent Form and applicable laws (e.g., health authority requirements).

The repository specimens will be subject to the confidentiality standards (as described under Confidentiality and in [Appendix 1](#)).

## **8.9           HEALTH ECONOMICS**

Health Economics/Medical Resource Utilization and Health Economics parameters are not evaluated in this study.

## **8.10          TIMING OF STUDY ASSESSMENTS**

### **8.10.1       Screening and Pre-treatment Assessments**

Written informed consent for participation in the study must be obtained before performing any study-specific screening tests or evaluations. Informed consent may be obtained up to 3 months prior to randomization. Screening start will be defined as the first assessment done after signature of the informed consent form. Informed Consent Forms (ICFs) for enrolled participant and for participants who are not subsequently enrolled will be maintained at the study site.

All screening and pre-treatment assessments must be completed and reviewed to confirm that participants meet all eligibility criteria. The Investigator will maintain a screening log to record details of all participants screened and to confirm eligibility or record reasons for screening failure.

An Eligibility Screening Form (ESF) documenting the Investigator's assessment of each screened participant with regard to the protocol's inclusion and exclusion criteria is to be completed by the Investigator and kept at the investigational site.

Screening and pre-treatment assessments will be performed within 35 days prior to Day 1 unless otherwise specified.

### **8.10.2       Assessments during Treatment**

Under no circumstances will participants who enroll in this study and have completed treatment as specified, be permitted to be allocated a new randomization number and re-enroll in the study.

All assessments must be performed as per SoA (see Section [1.3](#)). Assessments scheduled on the day of study treatment administration should be performed prior to administration of study treatment, unless otherwise noted in the schedule of activities. COA assessments (Section [8.2.7](#)) should be performed prior to the completion of other study assessments.

### **8.10.3 Assessments at Study Completion/Early Termination Visit**

Participants who complete the study (defined in Section 4.4) will be asked to return to the clinic 56 days after the last dose of study drug for a follow-up visit.

Participants who discontinue from the study early will be asked to return to the clinic 28 days after the last dose of study drug for a follow-up visit.

### **8.10.4 Follow-Up Assessments**

After the study completion/early termination visit, AEs should be followed as outlined in the SoA (Section 1.3) and in Sections 8.3.1 and 8.3.3.

Participants positive for ADAs at the study completion/early termination visit will be asked to return for further ADA assessments.

### **8.10.5 Assessments at Unscheduled Visits**

Please see Section 1.3 for activities that are required to be performed in case of an unscheduled visit.

## **9. STATISTICAL CONSIDERATIONS**

### **9.1 STATISTICAL HYPOTHESES**

Not applicable.

### **9.2 SAMPLE SIZE DETERMINATION**

The study will enroll up to 65 participants to assess the safety and tolerability of repeated dosing of RO7049665 (approximately 10 participants, randomized in the ratio of 4:1 RO7049665 to placebo, per cohort).

The sample size for this study was selected on the basis of clinical judgment and practicality. It was not determined on the basis of power against a formal statistical hypothesis. However, with a full cohort of 8 participants treated at a given dose level, there is an 83% chance to observe at least one AE that has a true incidence rate of 20% at that dose level in the population. After 4 participants have been treated at a given dose level, there is a 59% chance of observing such an AE.

### 9.2.1 Populations for Analyses

For purposes of analysis, the following populations are defined in [Table 6](#).

**Table 6 Analysis Populations**

Population	Description
Intent-to-treat (ITT)	All randomized participants will be included in the intent-to-treat population.
Per-protocol (PP)	All randomized participants that received the expected number of doses will be included in the per-protocol population.
Safety	All participants randomized to study treatment and who received at least one dose of the study treatment, whether prematurely withdrawn from the study or not, will be included in the safety analysis.
Pharmacokinetic	Participants who have received active treatment will be included in the PK analysis population. Participants will be excluded from the PK analysis population if they significantly violate the inclusion or exclusion criteria, deviate significantly from the protocol, or if data are unavailable or incomplete which may influence the PK analysis. Excluded cases will be documented together with the reason for exclusion. All decisions on exclusions from the analysis will be made prior to database closure.
Efficacy	Participants who were included in the ITT population.
Pharmacodynamic	Participants who were included in the Safety analysis population.
Biomarker	Participants who were included in the Safety analysis population.
Immunogenicity	Participants who had at least one pre-dose and one post-dose ADA assessment will be included and analyzed according to the treatment they actually received. In first instance, only samples from RO7049665-treated participants will be analyzed. The relationship between ADA status and safety, efficacy, PK, and biomarker endpoints will be analyzed and reported descriptively.

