Immunogenicity was assessed, and positive results for anti-drug antibody (ADA) were observed in a total of 12 participants starting from Cohort 5 (dose of 190 µg). ADAs were of early onset (detected in first samples on Day 8 post-dose), generally transient, and exhibited dose dependency with regard to titers and incidence. The presence of ADA had no apparent impact on the safety, PK and PD profiles. Further analysis was performed and concluded that the ADAs were not capable of neutralizing recombinant human IL-2.

Serum RO7049665 concentration reached peak level ( $C_{max}$ ) approximately 12 hours post-dose and declined in an apparent biphasic manner, with a mean apparent terminal phase half-life of approximately 72 to 137 hours (see [Table 3](#)). Serum exposure levels of RO7049665 were below or close to the detection limit in the 1.5 and 5µg dose groups and thereafter increased with increasing doses in a highly variable manner. Overall, no obvious deviation from dose-linearity was noted. Sufficient concentration data for reliable estimates of non-compartmental parameters in terms of both AUC and  $C_{max}$  was available as of cohort 6 (650 µg) and above (see [Table 3](#)). Although the data showed moderate between-subject variability, no relevant departure from linearity was noted. The mean serum apparent systemic clearance of RO7049665 appeared dose-independent and ranged from 1.4 to 2.2 L/h.

RO7049665 disposition occurred with a mean  $T_{1/2}$  of about 5 days, thus is expected to approach near-complete washout ( $C_{trough} < 10\%$  of  $C_{max}$ ) no later than 2 weeks post last dose. Accordingly, no substantial accumulation in reaching steady state is expected in a biweekly regimen.

At the highest dose of 7500 µg RO7049665, exposure was 33% and 65% of the exposure at the no-observed-adverse-effect level (NOAEL) (established in female monkeys on Day 22) in terms of  $C_{max}$  and  $AUC_{0-168h}$ , respectively.

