### **8.2.6 Immunogenicity Assessments**

Blood samples for ADA will be taken as described in the SoA (Section 1.3). The date and time of each sample will be recorded in the eCRF. Additional samples will be taken in participants with clinical signs of hypersensitivity reaction for ADA evaluation (see SoA Section 1.3). In each case, for each collected ADA sample, a corresponding PK sample will be collected at the same time-point for the determination of the RO7049665 concentration (See Section 8.5). Additional ADA sampling may be required after the safety and follow-up visit (Day 99) for participants who are ADA positive at the Day 99 visit. In this instance no corresponding PK sample is needed, however a sCD25 sample should be taken.

Validated ADA assays will be employed to detect ADAs against RO7049665. Samples which are positive for ADA will be further characterized and their neutralizing capability for recombinant IL-2 will be assessed using the neutralizing antibody (Nab) assay.

If required, remaining ADA samples may also be used for assay development/validation experiments. For exploratory purposes such as epitope characterization or IgG-IgM-isotyping, samples may be analyzed by assays which are not fully validated. Such samples will be kept for up to 6 months after the finalization of the bioanalytical report.

Samples from placebo-treated participants may not be analyzed in the first instance, but retained for subsequent analysis if appropriate.

Details on sampling procedures, sample storage and shipment are documented in the sample handling manual.

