### **9.3.5 Immunogenicity Analyses**

The immunogenicity analyses will include participants with at least one pre-dose and one post-dose ADA assessment.

The numbers and proportions of ADA-positive patients and ADA-negative participants during both the treatment and follow-up periods will be summarized.

- Participants are considered to be ADA positive if they are ADA negative at baseline but develop an ADA response following study drug administration (treatment-induced ADA response), or if they are ADA positive at baseline and the titer of one or more post-baseline samples is greater than the titer of the baseline sample by a scientifically reasonable margin such as at least 4-fold (treatment-enhanced ADA response).
- Patients are considered to be ADA negative if they are ADA negative at baseline and all post-baseline samples are negative, or if they are ADA positive at baseline but do not have any post-baseline samples with a titer that is greater than the titer of the baseline sample by a scientifically reasonable margin such as at least 4-fold (treatment unaffected).

The relationship between ADA status and safety, efficacy, PK, and biomarker endpoints may be analyzed and reported descriptively.

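### A single whole-study ADA label is related to exposure and safety with no time order, which dilutes any true link with exposure and can bias the link with hypersensitivity in either direction

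*Combined protocol and SAP*

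**What the plan says.** Section 9.3.5 classes each participant once. For those negative at baseline: "Participants are considered to be ADA positive if they are ADA negative at baseline but develop an ADA response following study drug administration". The negative class applies "if they are ADA negative at baseline and all post-baseline samples are negative". Those already positive at baseline are split by a titer rise, for example 4-fold. For a participant negative at baseline, one positive sample at any visit therefore fixes the label. No onset date, end date, or transient or persistent class is defined.

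Table 6 (Immunogenicity row) then uses the label: "The relationship between ADA status and safety, efficacy, PK, and biomarker endpoints will be analyzed and reported descriptively". Section 9.3.5 makes the same analysis optional: "The relationship between ADA status and safety, efficacy, PK, and biomarker endpoints may be analyzed and reported descriptively". Neither place says which samples count for which endpoint.

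Section 9.3.5 also says: "The numbers and proportions of ADA-positive patients and ADA-negative participants during both the treatment and follow-up periods will be summarized". This may mean a split by period, but it concerns incidence, not the association analysis.

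Section 8.2.6 adds samples after an event: "Additional samples will be taken in participants with clinical signs of hypersensitivity reaction for ADA evaluation". It also pairs a PK sample with every in-study ADA sample. Section 9.3.3 derives Cmax and AUC after the Day 1 dose and after the last dose. The last dose is on Day 43 (Section 4.1.1), so its two-week interval ends on Day 57. ADA sampling continues on Day 71 and Day 99.

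**The concern.** An antibody can affect only exposure that occurs while it is present. A whole-study label ignores this. Someone first positive on Day 71 is grouped with someone positive throughout dosing, and so is someone whose antibody had gone before Day 43. If these participants have the exposure of ADA-negative participants, they pull the positive group's mean towards the negative group's, and a real loss of exposure looks smaller than it is.

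For safety, the number of ADA samples depends on the outcome. A reaction triggers extra samples, which gives more chances to be positive. A second systemic reaction stops dosing (Section 4.1.4), and participants who discontinue early return 28 days after the last dose rather than 56 (Section 8.10.3), which gives fewer chances.

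Section 2.3 names hypersensitivity and reduced exposure among the risks of ADA. Section 2.2.2 reports almost complete loss of exposure in most low-dose monkeys after rapid ADA development. Section 2.2.2.1 reports ADA in about 50% of participants in this study so far, with no effect on exposure, and the projections in Section 4.3 assume none. An analysis that leans towards no effect is a weak check on that assumption.

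**Working it through.** **The plan's own figure.** The plan gives no figure for the ADA analysis. The detection probabilities in Section 9.2 reproduce: 1 − 0.8^8 = 0.832 and 1 − 0.8^4 = 0.590. They do not bear on this point.

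**Timing.**
- Median Tmax is about 12 h (Table 3). In the single-dose study ADA were first detected in the Day 8 samples (Section 2.2.2.1). A treatment-induced antibody therefore cannot act on Day 1 Cmax.
- A first positive on Day 71 or Day 99 comes after the last interval (Day 43 to Day 57) and cannot act on last-dose Cmax or AUCtau.
- The single-dose ADA were of early onset and "generally transient". Early onset makes late first positives rare. Transience makes clearance before Day 43 likely.

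**Dilution of the exposure ratio.** Let g be the true geometric mean ratio (positive to negative) among those whose antibody can act, and s the share of ever-positives whose antibody cannot. The expected observed ratio is g^(1 − s). Take g = 0.50 (assumed) and 8 scheduled post-baseline samples on Days 8, 15, 22, 29, 43, 57, 71 and 99 (read from a broken schedule table, so also an assumption).

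Share first positive after Day 57:

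| Onset assumption | s | Observed ratio |
|---|---|---|
| Early (Days 5 to 20) | 0 | 0.50 |
| Independent samples, 50% ever positive | (0.5^(6/8) − 0.5)/0.5 = 0.19 | 0.50^0.81 = 0.57 |
| Uniform to Day 99 | 0.32 to 0.44 | 0.50^0.68 = 0.62 to 0.50^0.56 = 0.68 |

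Early antibodies that clear: in a simulation with onset on Days 5 to 20, the share of ever-positives still positive on Day 43 or Day 57 was 0.024, 0.151 and 0.382 for mean antibody duration of 7, 14 and 28 days, and 0.873 for 200 days. If only these can affect the last dose, the observed ratios are 0.50^0.024 = 0.984, 0.50^0.151 = 0.901, 0.50^0.382 = 0.767 and 0.50^0.873 = 0.546.

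**Hypersensitivity with no true link.** Take 50% ever positive on 8 scheduled samples.
- *Independent samples (the extreme case).* The chance of at least one positive in k samples is 1 − 0.5^(k/8).
  - One triggered sample: 1 − 0.5^(9/8) = 0.541, odds ratio 1.18 (1.16 to 1.21 for 9 down to 7 scheduled samples).
  - Two triggered samples: 0.580, odds ratio 1.38 (1.33 to 1.44).
- *Antibodies present in one continuous spell.* Simulation: 55% have a spell, mean length 7 to 200 days, 15% have a reaction unrelated to ADA, one triggered sample each, no early stopping. Odds ratio 0.99 to 1.03. A triggered sample changes the label only if it is the sole positive.
- *Reactors stop after dose 2*, with about 5 samples in all including two triggered (assumed), independent samples: 1 − 0.5^(5/8) = 0.352, odds ratio 0.54 (0.47 to 0.64).

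**Precision.** With 65 × 0.8 = 52 on active treatment and about half positive, the groups are 26 and 26. Using the 55.4% CV for AUCinf at 7.5 mg (Table 3), the 95% interval spans a factor exp(t × √ln(1 + 0.554²) × √(2/n)) each way: 1.33 for 26 against 26, and 2.45 for 4 against 4.

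**The case against.** The analysis is descriptive and no hypothesis is tested. The ADA endpoint in Table 4 is incidence, which an ever-positive label serves well. The association is optional in Section 9.3.5. ADA and PK results will be listed, so a careful reader could match them by hand, and nothing says a positive-or-negative split is the only display. All of this stands and limits the weight of the point. It does not supply a time-matched analysis, because the only ADA status the plan defines is the whole-study one.

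Stronger readings are tempting, but the documents do not support them:
- *The hypersensitivity link is inflated.* This needs samples that behave as independent draws. With antibodies that persist across visits the effect is about nil, and early stopping of reactors can reverse it.
- *A large share convert after the last interval.* No document gives such a share. The only onset data, from single doses, point to early onset.
- *Sampling after Day 99 distorts the label.* Section 8.2.6 takes those samples only from participants already positive at Day 99.
- *The case for 15 mg rests on this label.* The amendment rationale argues from no clear relationship between ADA and dose. The statement that ADA did not affect exposure is in Section 2.2.2.1, which the rationale cross-references, and nothing shows which ADA definition produced it.

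It can also be objected that classing reactions only by the last scheduled result before onset would discard the sample taken at the reaction, the most informative one. That is right, and the fix below keeps it.

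**Conclusion.** The point holds. For exposure, the rule in Section 9.3.5 combined with Table 6 dilutes any true ADA effect towards none. The direction follows from timing, on two assumptions: participants whose antibody is absent during an interval have the exposure of negatives, and first detection is a fair stand-in for first presence. The size is unknown. It depends on onset and persistence under repeat dosing, which the documents do not report. If single-dose behaviour carries over, the main source is antibodies that clear early rather than late first positives. The ratios shown rest on an assumed true ratio of 0.50 and are illustrations, not estimates.

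For hypersensitivity, the association may be biased in either direction, and the reader could not tell which way to correct it. This is a weakness in a secondary, descriptive analysis. It does not touch the primary safety summaries or ADA incidence.

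**What to change.** In Section 9.3.5 and Table 6:

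1. Keep ever-positive status as the incidence summary, and show treatment and follow-up periods separately.
2. Relate PK to time-matched ADA status: the predose result on Days 15, 29 and 43, and results within the same dosing interval, with the paired PK samples. Use trough and peak values for doses 2 and 3, which Section 9.3.3 already plans to plot, and Cmax and AUCtau for the last dose. Confirm in the schedule that the 12-hour samples exist for doses 2 and 3.
3. Do not relate post-baseline ADA status to Day 1 Cmax.
4. For safety, show ADA onset relative to event onset. Give the association with and without event-triggered samples, and list those samples rather than discard them.
5. Make Table 6 and Section 9.3.5 agree on whether the association analysis will or may be done.

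The cost is wording and some programming. No new visits, samples or participants are needed. The drawback is smaller groups at each time point, so intervals will be wide and the analysis stays descriptive.
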